
Study Design
 
This study is designed as a multicenter, randomized, double-blind, active- and placebo-controlled study to compare the anti-tetanus neutralizing antibody titers and safety of TNM002 Injection with HTIG or placebo following a single IM injection, and determine the dose of TNM002 Injection for tetanus prophylaxis in phase III clinical study. The study will be conducted at approximately 5-10 study centers, and approximately 240 Chinese male or female adult volunteers are planned to be enrolled. Eligible volunteers will be randomized in a ratio of 2: 2: 1: 2: 1 to TNM002 Injection 5 mg, TNM002 Injection 10 mg, TNM002 Injection 15 mg, HTIG 250 IU, and placebo groups. At randomization, the volunteers will be stratified by the rapid test results of tetanus antibody IgG (negative and positive), and the proportion of volunteers with negative test results is at least 50%. The study drug and number of volunteers in each treatment group are shown in the table below.
 
  
 Group	Number of Volunteers	Drug for Injection	Dose	Dose Volume	
   
 1	60	TNM002 Injection	5 mg	0.25 mL	
 
 2	60	TNM002 Injection	10 mg	0.5 mL	
 
 3	30	TNM002 Injection	15 mg	0.75 mL	
 
 4	60	HTIG Injection	250 IU	2.5 mL	
 
 5	30	Placebo	NA	0.5 mL	
  
 
This study will consist of a screening period (D-28 to D-2), an in-patient period (D-1 to D4), and a follow-up period (D5 to D106). Eligible volunteers will be admitted to the study site on D-1. After completing the relevant tests required by the protocol and randomization, all volunteers will receive the study drug on D1. Dispensing and administration of the study drug will be performed by unblinded study personnel, and the injection time of all study drugs should be controlled within 30 (\pm 3) seconds. After dosing, volunteers will undergo the safety assessment at the study site, including physical examination, vital signs, 12-lead ECGs, and laboratory tests (hematology, blood chemistry, and urinalysis). At the same time, the investigator will also collect serum samples at specified time points for anti-tetanus neutralizing antibody titers, PK, and immunogenicity analysis. Safety results on D-1 are defined as the baseline of safety assessment, and anti-tetanus neutralizing antibody titers, PK, and immunogenicity analysis results of serum samples collected prior to dosing on D1 are defined as the baseline of the relevant assessment. Volunteers will be discharged from the hospital after completing safety assessment and serum sample collection on D4. After completing the blood collection at 48 hours post-dose and safety assessment during the in-patient period, the subject can be discharged early at the comprehensive judgment of the investigator.
 
Volunteers will return to the study site on Days 7, 14, 21, 30, 60, 90, and 106 for safety assessment and/or serum sample collection for anti-tetanus neutralizing antibody titers, PK, and immunogenicity analysis. The visit on D106 is considered as the end of study (EOS) visit, during which the volunteers will undergo a comprehensive safety assessment.
	Group	Number of Volunteers	Drug for Injection	Dose	Dose Volume	1	60	TNM002 Injection	5 mg	0.25 mL	2	60	TNM002 Injection	10 mg	0.5 mL	3	30	TNM002 Injection	15 mg	0.75 mL	4	60	HTIG Injection	250 IU	2.5 mL	5	30	Placebo	NA	0.5 mL

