Exclusion Criteria	
Volunteers who meet any of the following criteria will be excluded from the study:
 
 1) History of allergy to the investigational product, human immunoglobulin preparation or any component of other therapeutic monoclonal immunoglobulins; 2) History of chronic eczema or urticaria or multiple drug allergies; 3) History of blood phobia or needle sickness; 4) History of acute infection within 1 week prior to screening; 5) Previously diagnosed or suspected immunodeficiency or autoimmune disease; 6) Exposure to tetanus vaccine within the 10 years; 7) Receipt of an immunoglobulin or blood products within 6 months prior to dosing; 8) Exposure to any live attenuated or inactivated vaccines (including COVID-19 vaccine) within 4 weeks prior to dosing or plan to receive such vaccines within 3 months after dosing; 9) Use of any new drug therapy within 2 weeks or 5 drug half-lives (whichever is longer) prior to screening; 10) Known or suspected history of drug abuse within the past 5 years or a previous history of drug addiction or with positive urine drug test; 11) History of significant alcohol abuse within 6 months prior to screening, or any indication of regular use of more than 14 units of alcohol per week (1 unit = 360 mL of beer or 45 mL of alcohol 40% or 150 mL of wine); 12) Participation in any clinical studies with drugs or device within 3 months prior to screening, or ≤ 5 elimination half-lives (whichever is longer) from the last dose of the investigational drug, except for participation in clinical studies that do not use the investigational drug or device after screening or the observational, non-interventional studies; 13) History of clinically significant bleeding disorders (e.g., coagulation factor deficiency, coagulation defects, or platelet disorder); 14) Scars, tattoos, rash at the injection site that affect the administration or assessment; 15) Positive for human immunodeficiency virus (HIV) or hepatitis C virus (HCV) antibodies, or treponema pallidum-specific antibody or hepatitis B surface antigen (HBsAg) at screening; 16) Ear temperature $> 37.5^{\circ}\text{C}$, pulse rate > 100 beats/min or < 50 beats/min at screening; 17) For volunteers with no prior chronic disease or age < 60 years, systolic blood pressure (SBP) ≥ 140 mmHg or < 90 mmHg, and/or diastolic blood pressure (DBP) ≥ 90 mmHg or < 50 mmHg or ECG QTcF (heart rate-corrected) > 450 ms and/or other clinically significant abnormalities expected to be at significant risk for participating in the clinical study; 18) Laboratory tests: alanine aminotransferase (ALT) or aspartate aminotransferase (AST) > 2 ULN, total bilirubin > 1.5 ULN, decreases in haemoglobin (< 120 g/L in males and < 100 g/L in females), platelet count $< 120 \times 10^9/\text{L}$, white blood cell count $< 3 \times 10^9/\text{L}$, neutrophil count $< 1.8 \times 10^9/\text{L}$ or abnormal and clinically significant test results as judged by the investigator (except for the abnormal and clinically significant test results that can be explained by chronic disease); 19) Pregnant or lactating women; 20) Study personnel involved in the design and/or conduct of this study; 21) Other conditions that are considered to be not suitable for the study by the investigator.

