3. A serum (beta human chorionic gonadotropin [β -HCG]) pregnancy test will be performed for women of childbearing potential only.
4. Female volunteers who have not undergone hysterectomy or bilateral oophorectomy and have been menopausal for at least 1 year without other pathological or physiological reasons will undergo the serum FSH test to determine their post-menopausal status. The serum FSH test is not required for female volunteers of childbearing potential. Female volunteers with amenorrhea for less than 1 year should be considered fertile and do not require FSH test.
5. Viral serology tests include HBsAg, HCV antibody, HIV and treponema pallidum-specific antibodies.
6. If laboratory tests have been performed within 7 days prior to admission (D-8 to D-1), then the tests do not need to be repeated on D-1.
7. On D1 of the in-patient period, an injection reaction assessment will be performed 30 minutes (\pm 5 minutes) after IM injection of the study drug, and the local reactions at the injection site will be closely monitored and recorded.
8. The collection time of serum samples for anti-tetanus neutralizing antibody titers, PK and immunogenicity analysis are detailed in Section 8.2-8.4 of the text.

Statistical Analysis Plan

All statistical analysis will be performed using SAS version 9.4 or above.

The statistical analysis is mainly descriptive analysis. The continuous variables will be statistically described using the number of volunteers, mean, median, standard deviation (SD), minimum and maximum. The categorical and grade variables will be statistically described using frequencies and percentages for each category or grade, and missing values will not be included in the calculation of percentages unless otherwise stated.

No formal hypothesis testing will be performed on the data, but two-sided 95% confidence interval (CI) will be calculated based on $\alpha = 0.05$.

Statistical Analysis Population

- **Full Analysis Set (FAS):** all randomized volunteers who receive at least one dose of the study drug will be included in the FAS, which will be used for the analysis of volunteer disposition, demographics and baseline characteristics.

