Demographic data and other baseline characteristics will be analyzed descriptively by treatment group using descriptive statistics, and data will be tabulated and summarized.

Anti-tetanus neutralizing antibody titers Analysis

The number, percentage, 90% CI and 95% CI (based on the Clopper-Pearson method) of volunteers with an increase of anti-tetanus neutralizing antibody titers (Δ titers) ≥ 0.01 IU/mL from baseline at 24 hours post-dose will be calculated. The difference in the percentage of volunteers with Δ titers ≥ 0.01 IU/mL as well as 90% CI and 95% CI (based on the stratified Miettinen-Nurminen method, stratified by the rapid tetanus antibody IgG test results of at randomization stratification) of the difference between groups will be provided. Volunteers who withdraw from the study prematurely without detectable anti-tetanus neutralizing antibody titers at the respective time points will not be included in the analysis.

The anti-tetanus neutralizing antibody titers will be summarized by treatment group at each scheduled time point using the descriptive statistics, including number, median, minimum, maximum, geometric mean titer (GMT), geometric SD, 90% CI and 95% CI of GMT. In addition, the anti-tetanus neutralizing antibody titers at each scheduled time point after dosing will be compared and analyzed between treatment groups based on the mixed-effect model for repeated measures (MMRM). The MMRM model uses the log-transformed anti-tetanus neutralizing antibody titers (referred to as "log antibody titer") at each scheduled time point as the dependent variable, the treatment group, the rapid tetanus antibody IgG test results at randomization stratification, time point, and treatment group-time point interaction as the independent variables, and the intra-subject variance-covariance structure as the nonstructured variance structure (UN). The difference in log antibody titer and the 90% CI and 95% CI of the difference between different treatment groups will be calculated. The difference and corresponding CI of the difference will be antilog-transformed to obtain the ratio of GMT and CI of ratio between different treatment groups. If the model does not converge when the covariance structure is UN, other possible covariance structures, such as Toelitz, autoregression (1) (AR (1)), etc., can be selected, and the covariance structure with the smallest final AIC value will be used for the final model.

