The change from baseline in anti-tetanus neutralizing antibody titers at different time points post-dose and the proportion of volunteers with anti-tetanus neutralizing antibody titers ≥ 0.01 IU/mL and ≥ 0.1 IU/mL, ≥ 0.01 IU/mL and ≥ 0.1 IU/mL increase from baseline in anti-tetanus neutralizing antibody titers, ≥ 0.01 IU/mL increase from baseline in anti-tetanus neutralizing antibody titers at 24 hours and on Day 30 post-dose in different treatment groups will be summarized and compared using a similar statistical analysis method.

The duration of Δ titers ≥ 0.01 IU/mL post-dose from baseline is defined as the time interval from the first to the last observed increase of Δ titers ≥ 0.01 IU/mL from baseline. Subjects whose Δ titers remain ≥ 0.01 IU/mL at the last test time point of the study will be considered

censored in duration calculation. The median duration, corresponding two-sided 90% CI, 95% CI, minimum and maximum will be estimated using the Kaplan-Meier method. The duration between different treatment groups will be compared using the Cox proportional hazards model, which will include the treatment groups and the rapid tetanus antibody IgG test results at randomization stratification. If the censoring proportion is low, a descriptive summary of duration will be considered and the duration between different treatment groups will be analyzed based on an analysis of covariance (ANCOVA) model, which will include the treatment groups and the rapid tetanus antibody IgG test results at randomization stratification. The duration of Δ Titers ≥ 0.1 IU/mL post-dose from baseline will be analyzed using the same analytical method.

If data are applicable, the subjects will be divided into two subgroups (<0.01 IU/mL and ≥ 0.01 IU/mL) based on the test results of anti-tetanus antibody in serum samples collected prior to dosing to repeat the above analysis.

The anti-tetanus neutralizing antibody titers at baseline, the post-baseline anti-tetanus neutralizing antibody titers at each time point and the change from baseline in anti-tetanus neutralizing antibody titers will be tabulated by treatment group.

Safety Analysis

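### The log-titre MMRM leaves out the measured pre-dose titre, so the secondary GMT ratios against HTIG and placebo, and usually those between TNM002 doses by Day 90, are less precise than the collected data allow

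*Combined protocol and SAP*

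**What the plan says.** The model is in the Statistical Analysis Plan, under Anti-tetanus neutralizing antibody titers Analysis. Log titre at the scheduled time points is regressed on "the treatment group, the rapid tetanus antibody IgG test results at randomization stratification, time point, and treatment group-time point interaction as the independent variables", with "the intra-subject variance-covariance structure as the nonstructured variance structure (UN"). Other structures are used only if that one does not converge. The rapid test thus has one effect common to all visits, the pre-dose titre does not appear, and the covariance is not grouped by arm. For the output, "The difference in log antibody titer and the 90% CI and 95% CI of the difference between different treatment groups will be calculated" and then back-transformed to GMT ratios. This covers every pair of arms, placebo included.

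The baseline value exists. Under Study Design, results of "serum samples collected prior to dosing on D1 are defined as the baseline of the relevant assessment". Randomisation is stratified by the rapid test, and "the proportion of volunteers with negative test results is at least 50" per cent, so up to half of the volunteers may be positive. Exclusion Criteria, item 6, removes "Exposure to tetanus vaccine within the 10 years", which may narrow the spread of pre-dose titres.

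The titer analysis uses baseline in two other places. Rises from baseline are compared between arms by a similar method. If the data allow, volunteers are also split at 0.01 IU/mL "based on the test results of anti-tetanus antibody in serum samples collected prior to dosing to repeat the above analysis".

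On status, the SAP states that "No formal hypothesis testing will be performed on the data". Sample Size Estimation gives no variance or effect size.

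**The concern.** After a passive antibody injection, the measured titre is the volunteer's own antibody plus the injected antibody. Own antibody is almost the whole titre under placebo, a sizeable part under a product that adds little, and a small part at a high dose shortly after injection. Where the share is large, the pre-dose titre predicts the post-dose log titre well, and omitting it leaves explainable variation in the residual. A two-level rapid test cannot capture variation within each stratum.

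At stake is the precision of the planned model-based comparison of titre levels between doses, HTIG and placebo, with 30 to 60 volunteers per arm, in a study meant to choose the phase III dose. The missing information has already been collected.

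**Working it through.** **Inputs from the documents.** Allocation 2:2:1:2:1 of 240 gives 240 × 2/8 = 60 and 240 × 1/8 = 30, which matches the group table. The flow chart has 10 post-dose titre sampling days. No titre level, SD, correlation or half-life is stated, so the plan has no precision figure to reproduce and every size below is assumed.

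**Mechanism.** With own titre B and injected titre P, the slope of log(B + P) on log B is B/(B + P). As an illustration from the assumed grid, take B = 0.02 IU/mL, 61% of peak reached at 24 h, and peak rises of 0.25 (5 mg), 0.50 (10 mg) and 0.05 (HTIG):
- 10 mg: 0.02/(0.02 + 0.305) = 0.06
- 5 mg: 0.02/(0.02 + 0.1525) = 0.12
- HTIG: 0.02/(0.02 + 0.0305) = 0.40
- placebo: 1

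Baseline therefore matters little for early dose contrasts and much for HTIG and placebo contrasts.

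**Analytic check.** Adding a covariate with within-stratum correlation ρ multiplies the SE by √(1 − ρ²): 0.98 at ρ = 0.2, 0.87 at 0.5, 0.71 at 0.7 and 0.44 at 0.9.

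**Grid simulation.** There were 864 assumed sets with 400 complete-data trials each, the planned arm sizes, 10 visits and balanced strata. Varied inputs were:
- baseline median 0.005 or 0.02 IU/mL in negatives, and 2.5, 10 or 50 times that in positives; total log10 SD 0.23 to 0.94
- negative share 50, 70 or 90%
- between-subject log SD of the rise 0.3, 0.5 or 0.9
- assay CV 10 or 30%
- peak rise for 5 mg 0.1, 0.25 or 0.5 IU/mL; 10 and 15 mg two and three times that; HTIG 0.05, 0.05 or 0.1

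Absorption (61% of peak at 24 h) and half-life (25 days) were fixed. The alternative adds log pre-dose titre by visit and stratum by visit, with pooled covariance. The true sampling SD of the log ratio, planned over alternative, median (range), was:

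| Contrast | 24 h | Day 90 |
|---|---|---|
| 10 vs 5 mg | 1.00 (0.87–1.72) | 1.10 (0.90–2.95) |
| 10 mg vs HTIG | 1.03 (0.94–1.76) | 1.21 (0.99–3.12) |
| HTIG vs placebo | 1.22 (1.00–2.43) | 1.52 (1.03–4.16) |

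A ratio of 1.22 means a variance ratio of 1.22² = 1.49, so the planned analysis would need about 49% more volunteers for equal precision. The reported 95% CI width ratio was 1.10 at 24 h, 1.10 at Day 30 and 1.20 at Day 90 for practically every contrast, because the residual variance is pooled. It is not a measure of real gain: 10 vs 5 mg at 24 h has width ratio 1.10 but sampling-SD ratio 1.00.

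A smaller check (8 assumed sets, 800 trials each) gave 0.95–0.98 at 24 h and 0.95–1.00 at Day 30 for 15 vs 10 mg, so adjustment was equal or slightly worse there. No sampling-SD ratio is available for 15 vs 10 mg at Day 90.

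**Which term gives the gain.** A separate simulation used 7 scenarios, 200 trials each, six visits and varied absorption. Stratum by visit alone left the sampling SD unchanged. In the low-baseline scenario at Day 90, 10 mg vs HTIG had 0.103 with and without it; only the model SE moved, from 0.123 to 0.119. Adding pre-dose titre by visit brought the sampling SD to 0.083, a ratio of 0.103/0.083 = 1.24. A single baseline slope for all visits raised the model SE by up to 34% at early visits in one scenario.

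**Timing.** The model-SE loss was largest at Day 90 in 5 of the 7 scenarios. With slow absorption (the other 2) it was largest at 24 h. In one of these, 10 mg vs HTIG had sampling-SD ratios of 0.133/0.082 = 1.62 at 24 h, 0.113/0.088 = 1.28 at Day 30 and 0.141/0.092 = 1.53 at Day 90.

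**Bias.** The largest mean error in the grid was 0.03 log units, within simulation noise.

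**Coverage of 95% intervals with model-based SEs** (Monte Carlo SE √(0.95 × 0.05/400) = 0.011). For HTIG vs placebo at 24 h the planned model covered 0.95 (0.70–1.00), under 0.925 in 34% of sets; in those sets the alternative raised the median from 0.87 to 0.93. For 15 vs 10 mg at Day 90, coverage moved from 0.98 to 0.94, and the share of sets under 0.925 rose from 6% to 29%. The alternative's terms with arm-specific variances covered 0.91–1.00 for the five contrasts studied at 24 h, Day 30 and Day 90.

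**The case against.** **Baseline is already used elsewhere.** The primary endpoint and several secondary ones are rises from baseline, and subtraction removes own antibody directly on the additive scale. The subgroup repeat also lets effects and covariance differ by baseline category. This stands as partial cover. But a comparison of rises is not a GMT ratio of titres, and the repeat is conditional and gives two sets of ratios rather than one adjusted ratio. If the pre-dose sample were meant to enter as one of the modelled time points, the free treatment-by-time means would still leave complete-data contrasts unadjusted.

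**The spread of baseline may be small.** With a total log10 SD below 0.35, the median CI width ratio is only 1.03 at 24 h and 1.08 at Day 90. This stands: the gain could be minor.

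**Dose contrasts barely change before Day 90, and the alternative has its own fault.** One baseline slope per visit is shared by all arms although the mechanism implies different slopes, and late 15 vs 10 mg intervals can become too short. Both points stand and limit the claim.

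**The single rapid-test effect.** A reader might infer that giving the rapid test one effect for all visits itself costs precision. Randomisation is stratified, so arms are balanced on it, and letting the effect vary by visit changed the model SE but not the sampling SD.

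**Conclusion.** The point holds in a limited form and is worth considering. The model omits a collected baseline value, and the GMT ratios against HTIG and placebo, and usually those between doses by Day 90, lose precision. The loss is clearest against placebo (median sampling-SD ratios 1.22 and 1.52) and modest against HTIG at 24 h (1.03), where a few sets show none. The Day 90 statement for dose contrasts rests on 10 vs 5 mg. For dose contrasts at earlier visits the gain may be nil or slightly negative.

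A reader might infer three stronger things that the documents do not support:
- **The loss falls mainly at later visits.** That depends on kinetics the documents do not give, and slow absorption reverses it.
- **The ratios are biased or the conclusions invalid.** No bias appeared. The comparison is secondary and descriptive, no stated decision rule uses these intervals, and the primary 24 h proportion does not come from this model.
- **The planned intervals are generally too wide for active arms and too narrow against placebo.** That needs widely spread pre-dose titres. With a log10 SD below 0.35, planned coverage for 10 vs 5 mg at 24 h was 0.95 (0.91–0.99).

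Confidence is medium: the omission is plain from the text, but its size and timing depend on how much of the post-dose titre is the volunteer's own antibody.

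**What to change.** Before unblinding:

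1. Add log pre-dose titre to the MMRM with a separate slope at each visit, not one common slope. Add rapid-test stratum by visit as an accompanying term, whose main effect is on the model SE.
2. Fix a substitution value for pre-dose titres below quantification, and name the SE and degrees-of-freedom method (for example Kenward-Roger).
3. As a sensitivity analysis, fit the same terms with arm-specific covariance, using a simpler structure if it does not converge. Read the placebo and 15 mg contrasts with it.
4. Keep interactions of stratum or baseline with treatment exploratory. Even with arm-specific variances they covered only 0.76–0.98 for placebo contrasts, and at 90% negative a 30-volunteer arm has about 30 × 0.10 = 3 positives.

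**Cost.** SAP wording and programming, with no new data. Fixed effects rise from 5 × 10 + 1 = 51 to 50 + 10 + 10 = 70. An unstructured matrix has 10 × 11/2 = 55 parameters, and five arm-specific ones have 275, which is why that fit is only a sensitivity analysis. The statistical downside is that, with pooled covariance, 15 vs 10 mg intervals can fall below nominal coverage, most clearly at late visits.
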